#### **4.6.2 ITFPS-2 Recruitment Protocol**

The sites will begin recruitment on a rolling basis over a 9-week period. In the 1st week we will launch recruitment in 5 sites, in the 2nd-8th week we will launch in 10 sites weeks; and in the 9th week we will launch in 5 sites. Recruitment will be conducted over a 4.5 months. Figure 4-5 illustrates the recruitment protocol. The first step will be for a WIC staff person to identify a new WIC enrollee. From talking with the sites we understand that this will be a simple process for staff particularly because these participants have to be enrolled into the management information system. Based on our discussions with sites and Altarum's experience working with WIC programs in 31 States and over 200 clinics, we understand that the WIC enrollment process in most sites starts with a WIC staff person obtaining key information from the person seeking to enroll. This includes household family size and income, residence, and identification. The staff person will assess the income and residence information to determine if the applicant meets income and residence/service area requirements. The applicant will then participate in a nutrition assessment, including anthropometric and blood tests, to determine nutritional risk and, if they are determined eligible for the WIC program they will receive nutrition education and a food package. If the enrollee comes into the service site to enroll, the WIC staff person will identify all pregnant women in the designated study enrollment window who are enrolling in WIC for the first time for their current pregnancy and all infants less than 2.5 months whose mothers did not enroll prenatally. They will complete a 2-ply referral form that includes WIC ID, name, contact information, pregnancy status, age, and language. One copy will go to the woman (yellow); the other will be saved for the Westat recruiter/helper who will collect the forms at the end of the day. The Westat recruiter/helper will look for women holding a yellow referral form and attempt to intercept her at the end of her WIC visit in order to introduce

Figure 4-5. Recruitment flow

the study and screen the woman.. The strategy for notifying the recruiter/helper will be refined at each site, but the basic method is to have the Westat field recruiter/ helper look for the women with a yellow referral form and talk to them about the study once WIC business is conducted. In order to ensure that the participant has been determined to be eligible for WIC and to make sure that there is no impact (real or perceived) of the study on the receipt of WIC benefits, the determination and flagging will occur at the end of the participant's WIC appointment. Westat will not approach the participant until she has completed all of their WIC business. The recruitment should not interfere with or interrupt any participants being certified, receiving benefits, or receiving nutrition education or breastfeeding support. For example, this includes interruptions or delays to the flow of WIC appointments and being approached in the waiting room when WIC business has not been completed. Furthermore, the recruitment will not, directly or indirectly, impact or change clinic hours (example: M-W, 8am-5pm) or clinic schedules (example: M-W are certification appts, Thu-Fri are nutrition education).

Once a Westat field staff (recruiter/helper) makes contact with the woman they will find a pre-determined private place, and introduce the *Feeding My Baby Study* by showing the woman the study flyer. In addition they will explain that to participate in the study the woman will need to answer some questions that day and will be contacted by phone periodically to answer some questions about her baby's food consumption and feeding habits, until her child is two years old. The recruiter/helper will tell the woman that if she is confirmed to be eligible for the study, the interview today will take about 20 minutes and she will be compensated \$50; all future telephone calls will take no more than 30 minutes, and she will be compensated \$20 for each telephone interview. If the woman is interested and has time to spend talking about the study, she will be interviewed immediately in service sites that have a recruiter. In sites that have a helper, the helper will explain that the woman will be connected to a Westat telephone recruiter who will provide more detail about the study and will ask her some questions. The recruitment interview will take 20 minutes and the woman will be mailed \$50 for her time. Women who are interested but don't have time to spend at the clinic will be asked by the Westat field staff person for a good time and way to contact them to talk about the study. That information will be transferred to a Westat telephone recruiter who will contact them by phone.

The Westat recruiter (field or telephone) will administer a recruitment screener to determine whether the woman is eligible, and if so will obtain her consent and explain the HIPAA form and the need for a signature. They will administer the enrollment interview and obtain an address to send the incentive and study materials, and a telephone number to contact the participant for the follow-up interviews. If a woman cannot provide a contact telephone number the recruiter will ask if she needs

a cellphone. The Westat home office will send study materials, a cellphone (if needed), and the study incentive.

We expect there may be a very small number of women who will be enrolled in locations other than at the service site (e.g., hospital, mall, mobile vans). In those cases, the WIC staff will fill out a referral form and the Westat recruiter/helper will send the information to Westat. A Westat telephone recruiter will contact the woman.

### 4.6.3 Recruitment and Enrollment Steps

Participant enrollment at the service site is presented in Figure 4.5, and described below.

1. **Identify Eligible WIC Enrollees.** WIC staff will identify all pregnant women in the designated study enrollment window who are enrolling in WIC for the first time for their current pregnancy and all infants less than 2.5 months whose mothers did not enroll prenatally. They will complete a 2-ply referral form that includes WIC ID, name, contact information, pregnancy status, age, and language. One copy will go to the woman (yellow); the other will be saved for the Westat recruiter/helper who will collect the forms at the end of the day.
2. **Intercept on site.** The Westat recruiter/helper will look for women holding a yellow referral form and attempt to intercept her at the end of her WIC visit in order to introduce the study and screen the woman. Barring that, they will make sure the woman gets a study flyer with a toll-free number she can call to learn more about the study. Barring that, they will make sure the woman gets a study flyer with a toll-free number she can call to learn more about the study.
3. **Introduce Study.** A Westat recruiter/helper will take the woman to a private space (designated for the ITFPS-2 recruitment activity by the site) and introduce the study. This will involve providing the woman with a study flyer that explains what participation in the study entails, the incentives, and how the mother can play an important role in understanding the health of all infants by joining the study. If a woman expresses interest in participating in the study but does not have time to go through the recruitment process, the recruiter/helper will obtain contact information and a Westat telephone recruiter will contact her to introduce the study and determine whether she is eligible.
4. **Assign to Core or Supplemental Sample.** The screener instrument will be programmed to assign participants to either the core or supplemental group in an alternating pattern. For sampling purposes it is necessary to assign a woman to one of these groups before we screen her. (See Sampling Plan, Deliverable 8 for details). In sites that have a Westat field recruiter, the recruiter will assign interested new enrollees to the core or supplemental sample using a laptop; in sites where a Westat helper has

introduced the study, the helper will call a Westat number to make contact with a Westat telephone recruiter who will assign the woman to the appropriate sample.

5. **Administer Screener.** Westat recruiters (in-person or telephone) will administer the recruitment screener. In sites where the helper calls into the Westat telephone center to connect with a telephone recruiter, we will minimize wait time by monitoring call volume hourly during peak enrollment periods to ensure that all calls are picked up and linked with an interviewer immediately. When needed, we will be prepared to make adjustments to both the number of available toll-free staff and responsible interviewers.

The recruiter will confirm that the woman is eligible (i.e., has not been previously enrolled in WIC for her current pregnancy or that the infant is less than 2.5 months). Eligible respondents will be asked about their race, ethnicity, trimester of enrollment, pre-pregnancy BMI, household composition, and income. Core group participants will be retained irrespective of their responses to these questions. Participants assigned to the supplemental group may be found ineligible at this stage depending on their responses. Only rare population subdomains such as black mothers and infant who have no prenatal WIC exposure will be eligible for the supplemental group. Participants still eligible will also be asked questions to determine whether they plan to stay in the area during the study period, whether they are or will be the caregiver of the WIC infant, and their age. In addition, the interviewer will explain what participation involves; the number and types of interviews to be completed; and the incentive structure.

6. **Request Informed Consent and HIPAA Authorization.** The Westat recruiters will ensure the woman understands all aspects of the study, that her participation is confidential and voluntary, and her WIC services cannot be denied if she refuses to participate in the ITFPS-2. Consent procedures for mothers under age 18 vary by State, and will be determined based on the States identified for sampling. Women recruited in-person will sign the informed consent and receive a copy of the document for their records. Women recruited by telephone will provide verbal consent by agreeing to continue with the interview, and will receive a copy of the consent form through the mail. Westat recruiters will also request HIPAA authorization from participants assigned to the core group to allow access to medical records for enrolled women and their infants. Participants recruited in-person will sign the HIPAA form and receive a copy for their records; participants recruited by telephone will be sent a HIPAA form to be signed and returned in a postage-paid return envelope (see section 4.6.2. or 4-10).
7. **Administer Enrollment Interview.** Once a woman is determined eligible by the eligibility screener and has been recruited, the Westat field recruiter or Westat telephone recruiter will administer the enrollment interview which will collect detailed contact information (telephone numbers, email address, home address, contact information of friends and family members) and health data (due date if pregnant; name and birth date of infant if post-natal).
8. **Provide Cell Phone if Needed.** Since subsequent interviews will be by telephone, if a woman does not provide a phone number, a cell phone will be offered for the duration

of her participation. Westat will mail the phone to the participant prior to the first interview (i.e., prenatal, 1 month, or 3 months) with instructions on using it.

9. **Provide Incentive and Other materials.** Westat will send each participant an enrollment package that will include a \$50 incentive in the form of a debit card (which will be loaded with \$20 each time the participant completes an interview); a calendar with their interview dates; and measuring guides (for the 24-hour recall) to help them with the subsequent interviews. The measuring guides include measuring cups and spoons, a household teaspoon and tablespoon, and a ruler.

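### Core or supplemental assignment follows a predictable alternation with no concealment described, so core-only estimates are open to selection on race that the planned core weights do not adjust for

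*Combined protocol and SAP*

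**What the plan says.** Section 4.6.3 sets the order of events. WIC staff complete a referral form showing "WIC ID, name, contact information, pregnancy status, age, and language", the recruiter intercepts the woman and introduces the study, and only then does assignment take place (step 4). The screener is programmed to "assign participants to either the core or supplemental group in an alternating pattern". The section adds that "it is necessary to assign a woman to one of these groups before we screen her". At sites with a field recruiter, "the recruiter will assign interested new enrollees to the core or supplemental sample using a laptop"; where a helper is used, a telephone recruiter makes the assignment.

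The two groups have different retention rules (step 5). At screening, "Eligible respondents will be asked about their race, ethnicity, trimester of enrollment, pre-pregnancy BMI, household composition, and income". After that, "Core group participants will be retained irrespective of their responses to these questions", whereas "Only rare population subdomains such as black mothers and infant who have no prenatal WIC exposure will be eligible for the supplemental group". Step 6 has recruiters "request HIPAA authorization from participants assigned to the core group", so the recruiter knows which group each woman is in.

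Step 4 refers to the Sampling Plan (Deliverable 8) for detail. The documents in hand do not say that the next assignment is hidden, that women are approached in a fixed order, or that allocation is audited. They also do not say whether the alternation runs per site, per laptop or across a call centre.

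**The concern.** With strict alternation, knowing one assignment is enough to know the next. At field-recruiter sites, the person who knows it has also seen the woman and her referral form. The two groups treat women differently: a woman from a common group is kept in a core slot but may be screened out in a supplemental slot, while a black mother is kept in either. A recruiter who preferred not to turn away an interested woman could take a visibly rare woman first when a supplemental slot was due.

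If that happened, the core sample would hold too few of the groups that the supplement is meant to boost, and the core weights would not put this right:

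- The core base weight (Section 6.2) is built from site-level counts. It does not vary within a site and has no term for race.
- The nonresponse adjustment (Section 6.3) moves weight from nonrespondents to similar respondents. A swapped slot creates no nonrespondent.
- Race is not among the items that sites supply on every potentially eligible enrollee, and Section 6.3 rules out calibration to external totals.

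The exposed estimates are those that rest on the core alone. Table 6-1 gives only a core weight for the prenatal wave and for months 3, 5, 9, 11, 15 and 18. All the prenatal-views tables in Table 7-2 are core-only, and the first interim report rests on them.

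**Working it through.** **The plan's own figure.** Section 6.2 expects an average core weight on the order of 550. From its inputs, 2,000,000 × 0.78 / 2804 = 556.3. This reproduces, and the concern does not dispute it.

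**Implied retention.** Section 4.6 expects 55.4 recruits at each of 80 sites: 55.4 × 80 = 4432. Less 2804 core recruits, this leaves 1628 supplemental recruits. If the two halves are equal in size and in consent (an inference), mean retention in the supplement is 1628 / 2804 = 0.58.

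**Pair model.** Each pair of women fills one core and one supplemental slot. Let p be the share of women in a visible, always-retained group, and let s be the fraction of pairs with the rare woman due for core and the common woman due for the supplement that are swapped. Neither p nor s is in the documents.

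- Core share of the rare group: c = p − p(1 − p)s.
- Combined share, using the 1/(1 + r) weight of Section 6.2 with r = 1 for rare and r = 0 for common women: p / (p + 1 − c). Rare women are kept in either slot at half weight, so steering does not change their number. The remaining error comes from the extra common women in core at full weight.

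| p | s | core share (relative change) | combined share (relative change) |
|---|---|---|---|
| 0.2 | 0.10 | 0.2 − 0.016 = 0.184 (−8%) | 0.2/1.016 = 0.197 (−1.6%) |
| 0.2 | 0.25 | 0.2 − 0.04 = 0.160 (−20%) | 0.2/1.04 = 0.192 (−3.8%) |
| 0.2 | 0.50 | 0.2 − 0.08 = 0.120 (−40%) | 0.2/1.08 = 0.185 (−7.4%) |
| 0.1 | 0.25 | 0.0775 (−22.5%) | 0.0978 (−2.2%) |
| 0.4 | 0.25 | 0.340 (−15%) | 0.377 (−5.7%) |

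A simulation at p = 0.2, s = 0.25 gave 0.160 and 0.192. Over p = 0.1 to 0.4 at s = 0.25, the combined weight removes roughly 60–90% of the relative distortion (1 − 5.7/15 = 0.62; 1 − 2.2/22.5 = 0.90). Setting r = 0 for all other women is the worst case for the combined sample.

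**Effect on an outcome.** Suppose the groups differ by 15 points (assumed). At p = 0.2 and s = 0.25 the core bias is 0.04 × 15 = 0.6 points and the combined bias 0.12 points. The standard error of a 50% core proportion is 100 × √(0.25 × deff / 2804), which is 0.9 to 1.3 points for an assumed design effect of 1 to 2.

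**Opportunity.** Section 4.6 gives flows from 1.5 to 14 or more enrollees a day. With Poisson arrivals over an 8-hour day (assumed), the chance that another enrollee arrives within an hour is 1 − exp(−1.5/8) = 17% at the low end and 1 − exp(−14/8) = 83% at the high end.

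**The case against.** The strongest reply is that the documents do not show steering, and leave limited room for it.

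- The program sets the group before screening, so the answers cannot change it. Steering would require reordering or deferring women. Recruiters meet women as their visits end, and slow sites offer few simultaneous pairs. This stands as a limit on the size of the problem, but not at busy sites.
- No quota, per-recruit payment or target for recruiters is mentioned. Any incentive is inferred, and an implied mean retention of 0.58 means that most supplemental assignments are not lost. This stands.
- The retained groups are not all visible. Trimester, pre-pregnancy BMI and income cannot be judged reliably by sight. Black race and postnatal entry are the named examples that often can. This stands.
- Sites supply prenatal or postnatal status for every potentially eligible enrollee, so imbalance on that trait could be adjusted. Race remains.
- Section 7.5 prefers the combined sample wherever data exist, and most rows of Table 7-2 are marked for both samples. This protects the waves with a combined weight, not those for which Table 6-1 has a core weight only.
- The Sampling Plan may contain safeguards. That is possible, but the text in hand specifies alternation, which is not concealed random assignment.
- Alternation fixes the split within a site, and a simple half-probability draw would lose this. Permuted blocks largely keep it.

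**Conclusion.** The weakness is real but conditional. Assignment is predictable to someone who has met the woman, the groups have different retention rules, and no concealment is described. If women were reordered or deferred, core-only estimates could under-represent visible retained groups, chiefly black mothers, without correction by the core weights. With an assumed 20% rare share and 10–25% of the relevant pairs swapped, the core share falls by 8–20% in relative terms, but the combined share only by about 2–4%. The resulting bias in a core proportion is below one standard error under the assumptions shown at 25% swapping. Unlike sampling error, though, it would not shrink with sample size.

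A reader might infer more: that assignment is at the recruiter's discretion, that rare women will be steered out of core, or that no weight can repair the result. The documents support none of these. The program assigns, a motive and any actual steering are supposition, and the combined weight removes most of the distortion. The point is a cheap improvement, not evidence of a biased sample.

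**What to change.** 1. Replace the alternation in step 4 with permuted blocks of random size within site. Keep the next assignment hidden, reveal it only after the woman's WIC ID has been entered, and then lock it. Use the same lists for telephone recruiters. Predictability falls well below the 100% of alternation: even blocks of four with a known size allow about 71% correct guesses, (1/2 + 2/3 + 2/3 + 1)/4, and varying the size makes guessing harder.
2. Log women in referral order, so that order of approach can be checked. Referral forms show pregnancy status but not race.
3. Compare screener profiles between the groups by site, including women screened out of the supplement, since the items are asked before that decision. With about 98 screened per site (49 per group) and a 20% share, the standard error of the difference is √(0.32/49), about 8 points, so single-site results are weak. Pooled over 80 sites (3920 per group) it is √(0.32/3920), about 0.9 points. The modelled gap is 0.216 − 0.184 = 3.2 points at s = 0.10 and 0.24 − 0.16 = 8 points at s = 0.25. This assumes that all those screened answer the items.
4. If the Sampling Plan already provides these safeguards, state them in Section 4.6.3.

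The cost is a small programming change and slight chance imbalance within a site. Expected sample sizes (2804 core) and the mean weight (about 556) do not change. Concealment cannot be added afterwards, so this must be in place before recruitment starts.

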#### 4.6.4 Pre-Test Recruitment Protocol

We plan to test the recruitment protocol in the September -November 2012 timeframe at three different sites located in Los Angeles, Oklahoma, and Baltimore. The sites will be sampled into the study and will be chosen based on caseload and geographic location. While we will test the protocol at each site, we will not use WIC enrollees. The pretest will help us learn more about WIC sites. In particular, we will observe whether WIC site staff are able to accurately identify study eligible women and whether the referral form facilitates the entry of the information by WIC staff. We will also inspect the physical space available to accommodate enrollments by Westat staff while maintaining confidentiality. We will adjust our recruitment protocol as needed after conferring with FNS. We will also test prototypes of the data collection and communication tools we plan to use for recruitment (e.g., brochures/flyers, computer laptops, and cell phones) within these site environments to evaluate their feasibility. Details of our plans for pre-testing were delivered to FNS on September 11, 2012.

### 4.7 Conduct WIC Staff Surveys

Altarum will instruct staff to complete the WIC Staff Survey during the time period when participants are being recruited for the study. All staff persons at each WIC service site who have roles providing direct service to WIC participants (e.g., nutritionists, nurses, “competent professional authorities”, site supervisors, support/clerical staff, peer counselors and others) will be asked to complete a survey. The survey will be confidential and completed on-line or by hard copy

---

 Of note, the peer Advisory Panel (PAP) purposely recommended not sending participants the USDA Food Model Booklet (FMB) which includes pictures of glasses, cups, and bowls, since it might influence a WIC mother’s decision to begin solid foods earlier than appropriate. After discussion with [name] of the PAP, FNS agreed that the FMB was not needed to collect data on children between 1-11 months; however, they questioned whether this would affect a comparison of the toddler data to the NHANES data (where the FMB is used for this age group). Westat has requested the NHANES data to determine the extent the FMB is used to report portion sizes for 12-24 month olds.

(if the service site has no internet access). Altarum will introduce the survey to service site staff at the in-person visit conducted when site has been recruited. Staff will be informed of the process for accessing the survey and of the availability of a Support Desk if they have questions. To maximize response rates, Altarum will send periodic notes to the site supervisor or designated point of contact to advise them of the number of responses received with a request to remind staff to complete the survey. This survey will take about 30 minutes for each staff member to complete.

